9.2 Part 1, Arm B: EDT (letrozole and leuprolide)

MEMORIAL SLOAN-KETTERING CANCER CENTER IRB PROTOCOL

IRB#: 11-211 A(6)

Day 1 of Cycle 1: Baseline serum estrone, estradiol, testosterone and follicle-stimulating hormone (FSH) level in all patients (if not already done). If estradiol is within postmenopausal range for women (≤ 30 pg/mL) and testosterone is within the castration range for men (≤ 50 ng/dL), patient does not have to have hormones retested at week 2 and may begin letrozole 2.5 mg po QD Week 2 of Cycle 1.

- Day 1 of Cycle 1: Leuprolide 7.5 mg IM will be administered by a nurse in clinic.
- Week 2 of Cycle 1 (+/- 7 days): Women with estradiol not within postmenopausal range (≤ 30 pg/mL) or men with testosterone not within the castration range (≤ 50 ng/dL), measure serum estradiol and testosterone; if estradiol is within postmenopausal range (≤ 30 pg/mL) and testosterone is within the castration range (≤ 50 ng/dL), begin letrozole 2.5 mg po QD. Otherwise, retest hormones on C2W1. Consult MSKCC PI if hormones are still not within range. to further discuss the letrozole start date.
- Letrozole will be dispensed by the respective institutions' pharmacies and will be taken at home. Patients will be instructed to take letrozole at the same time each day, consistently with food or without food, and swallowed whole with a glass of water.
 - If a dose is missed, they will be instructed to take it as soon as they remember up until 12 hours past the schedule dose time. If it is almost time to take the next dose, they will be instructed to skip the missed dose and just take the scheduled dose. They will be instructed NOT to take 2 doses at the same time [137].
 - If vomiting occurs after taking letrozole, the subject should not take a replacement dose on that day. The subject should resume taking letrozole at the next scheduled dose on the following day. If vomiting persists, the subject should be instructed to notify the investigator. If a subject vomits what appears to be an intact tablet(s), the subject should not take a replacement dose on that day because it is not possible to determine how much drug has actually been absorbed.
 - Patients will be provided with a pill diary to record the date and time of day that letrozole was taken.
- Continue leuprolide 7.5 mg IM every 4 weeks (+/- 7 days).
- One cycle of EDT corresponds to 4 weeks of treatment.
- Letrozole and leuprolide should be administered concurrently at all times.
 - Patients who are able to tolerate only leuprolide, but not letrozole, will undergo serum estradiol and testosterone testing at the start of every cycle. If serum estradiol remains within the post-menopausal range (females) or within the castration range (males), therapy on leuprolide will continue.

- Patients who are able to tolerate letrozole, but not leuprolide, will be removed from the study. In very special circumstances (ie. postmenopausal female patient) study chair may allow continuation of letrozole alone pending the approval of the local IRB.
- Treatment will continue until disease progression, global clinical deterioration, unacceptable toxicity and/or consent withdrawal.
- EDT may be held for a maximum of 4 weeks to recover from toxicity (see Sections 9.6 & 9.7).

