4.3 Intervention

Patients randomized to Arm A will receive everolimus 7.5 mg PO QD.

Patients randomized to Arm B (EDT) will receive leuprolide and letrozole to provide central and peripheral suppression of estrogen production, respectively.

- Leuprolide will be administered as a monthly depot injection of 7.5 mg IM.
- Bloodwork will be drawn 1 week after the first injection of leuprolide to measure serum estradiol levels in females and serum testosterone levels in males.
- Letrozole 2.5 mg PO QD will be started 1 week after leuprolide is given if serum testosterone and estradiol levels are found to be within the castration range. Otherwise, initiation of letrozole will be delayed until week 4, coinciding with the second dose of leuprolide.

Patients randomized to Arm C (EDT + everolimus) will receive everolimus, leuprolide and letrozole at the same doses and schedule as outlined for Arms A and B.

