9.3 Part 1, Arm C: combined everolimus + EDT

- Day 1 of Cycle 1: Baseline serum estrone, estradiol, testosterone and follicle-stimulating hormone (FSH) level in all patients (if not already done). If estradiol is within postmenopausal range for women (≤ 30 pg/mL) and testosterone is within the castration range for men (≤ 50 ng/dL), patient does not have to have hormones retested at week 2 and maybe begin letrozole 2.5 mg po QD Week 2 of Cycle 1.
- Patients will begin leuprolide 7.5 mg IM and everolimus based on BSA:
 - Patients with a BSA $< 1.5 \text{ m}^2$ will receive everolimus 5 mg PO QD.
 - Patients with a BSA $\geq 1.5 \text{ m}^2$ will receive everolimus 7.5 mg PO QD.
- Week 2 of Cycle 1 (+/- 7 days): Women with estradiol not within postmenopausal range (≤ 30 pg/mL) or men with testosterone not within the castration range (≤ 50 ng/dL), measure serum estradiol and testosterone; if estradiol is within postmenopausal range for women or testosterone is within the castration range for men, begin letrozole 2.5 mg po QD. Otherwise, retest hormones on C2W1. Consult MSKCC PI if hormones are still not within range. to further discuss the letrozole start date.
- Leuprolide 7.5 mg IM will be given every 4 weeks (+/- 7 days).
- Everolimus and letrozole will be administered continuously using the same dose, schedule and administration instructions as outlined in sections 9.1 and 9.2. Patients will be given a pill diary to record the date and time that everolimus and letrozole were taken.
- One cycle of combined everolimus + EDT corresponds to 4 weeks of treatment.
- Everolimus, letrozole and leuprolide should be administered concurrently at all times. However, patients who are only able to tolerate everolimus and leuprolide, but not letrozole, can continue on therapy but need to undergo testing of serum estradiol and testosterone every 4 weeks. If serum estradiol remains within the post-menopausal range (in females) or castration range (males), therapy with leuprolide and everolimus continue.
 - Patients who are able to tolerate everolimus and letrozole, but not leuprolide, will be removed

from the study. In very special circumstances (ie. postmenopausal female patient), study chair may allow continuation of everolimus with letrozole pending the approval of the local IRB.

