- If everolimus or both EDT drugs must be completely discontinued, patient will be declared off trial. However, if a patient is able to tolerate either component of combined therapy (ie. Everolimus or EDT) but not both, and is experiencing clinical benefit, the study chair may allow continuation of everolimus or EDT pending the approval of the local IRB.
- Treatment will continue until disease progression, global clinical deterioration, unacceptable toxicity and/or consent withdrawal.
- Therapy may be held for a maximum of 4 weeks to recover from toxicity (see Sections 9.5 through 9.8)

9.4 Part 2: Combined therapy with everolimus and EDT after progression on either everolimus or EDT alone

- Patients who develop disease progression on either Arm A or B during Part 1 of the study will proceed to combined therapy.
 - At the start of Part 2 the last CT scan on Part I will be used as the baseline scan for RECIST 1.1 criteria.

Patients who were on everolimus (Arm A) during Part 1 will begin EDT with leuprolide 7.5 mg IM .

- Patients who required a dose reduction on Arm A during Part 1 will continue at the reduced dose level for Part 2.
- Day 1 of Cycle 1: Baseline serum estrone, estradiol, testosterone and follicle-stimulating hormone (FSH) level in all patients. If estradiol is within postmenopausal range for women (≤ 30 pg/mL) and testosterone is within the castration range for men (≤ 50 ng/dL), the patient does not have to have hormones retested at week 2 and maybe begin letrozole 2.5 mg po QD Week 2 of Cycle 1.
 - Week 2 of Cycle 1 (+/- 7 days): Women with estradiol not within postmenopausal range (≤ 30 pg/mL) or men with testosterone not within the castration range measure serum estradiol and testosterone; if estradiol is within postmenopausal range (women) or testosterone is within the castration range (men), begin letrozole 2.5 mg po QD. Otherwise, retest hormones on C2W1. Consult MSKCC PI if hormones are still not within range. to further discuss the letrozole start date.
 - Leuprolide 7.5 mg IM will be administered every 4 weeks (+/- 7 days).

Patients who were on EDT (Arm B) during Part 1 will begin everolimus on Day 1 of Part 2 of the study at the following doses:

- Patients with a BSA $\leq 1.5 \text{ m}^2$ will receive everolimus 5 mg PO QD.
- Patients with a BSA $> 1.5 \text{ m}^2$ will receive everolimus 7.5 mg PO QD.
- Patients should continue with their every 12 weeks hormone testing schedule from Arm B.

All Patients on Part II

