10.0 EVALUATION DURING TREATMENT/INTERVENTION

Treatment/Intervention	Anytime before C1D1	Within 4 wks of Tx	Within 2 wks of Tx	C1D1 ^a	C1W2 ^y	C1W3 ^f	C2W1 onwards ^b	C2W3 onwards ^b	Q4 wks	Q12 wks	4 wks after study
Study therapy											
Everolimus POQD ^c				x				Continuous administration			
Leuprolide 7.5 mg IM				x					x ^d		
Letrozole 2.5 mg PO QD					x ^e			Continuous administration			
Clinical											
History, physical exam, vitals, weight, ECOG versus Lansky as applicable, BSA			x		x ^v	x ^f	x	x ^f			x
Adverse event assessment				x	x ^v	x ^f	x	x ^f			x
Laboratory											
CBC +differential, metabolic panel ^g , Ca ²⁺ , PO ₄ , liver function tests ^h , LDH			x			x ^f	x ⁱ	x ^{i,f}			x
Ammonia ^w			x ^w	x ^w	x ^w	x ^w	x ^w	x ^w	x ^w	x ^w	x ^w
Hepatitis B sAg, cAb; +		x									
Quantitative PCR for hepatitis C and hepatitis B, (if known infection)			x ^j							x ^j	
Fasting glucose and lipid profile ^k			x			x ^l					x
Serum estrogens, testosterone, FSH			x	X ^{d,m,n}					x ^o	x	
Plasma neuropeptides, transcobalamin, DCP, AFP			x						x ^o		
Urinalysis ^p			x								
Serum pregnancy test			x ^q								
Imaging											
CT chest/abdomen/pelvis with contrast and triphasic liver ^r		x							x ^s		

MEMORIAL SLOAN-KETTERING CANCER CENTER
 IRB PROTOCOL

IRB#: 11-211 A(6)

Treatment/Intervention	Anytime before C1D1	Within 4 wks of Tx	Within 2 wks of Tx ^a	C1D1 ^a	C1W2 ^v	C1W3 ^f	C2W1 onwards ^b	C2W3 onwards ^b	Q4 wks	Q12 wks	4 wks after study
Other											
Blood sample for future research			x								
Pathology specimen ^t	x			Repeat if patient undergoes surgery							
Bone mineral density scan (patients \geq 16 years old)		x		Annually							
Bone age (all patients 12-15 yrs old) ^u		x		Every 6 months							
EKG			x	As clinically indicated							
Pulmonary function tests				As clinically indicated							
Psychiatric evaluation				As clinically indicated							

^a C1D1 = cycle 1 day 1; C1W2 = cycle 1 week 2

^b Continue same for all subsequent cycles

^c Patients with BSA $< 1.5 \text{ m}^2$ receive everolimus 5 mg PO QD. Patients with BSA $\geq 1.5 \text{ m}^2$ receive everolimus 7.5 mg PO QD. If BSA changes by $> 10\%$ above or below the 1.5 m^2 cut-off at any time during the study, the dose of everolimus must be adjusted accordingly.

^d May be done +/- 7 days

^e If estradiol (females) and testosterone (males) are within castration range. Otherwise, delay start of letrozole until week 4, coinciding with 2nd dose of leuprolide.

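### The Arm B week-2 rule for starting letrozole (9.2) requires both hormones in range with no sex label, while Arm C, Part 2, Arm B's own Day 1 rule and schedule footnote e are sex-specific

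*Combined protocol and SAP*

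**What the plan says.** Section 9.2 (Arm B) checks hormones twice before letrozole.

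- **Day 1 waiver.** The week-2 retest is skipped on a sex-labelled condition: "If estradiol is within postmenopausal range for women (≤ 30 pg/mL) and testosterone is within the castration range for men (≤ 50 ng/dL").
- **Week 2.** Women whose estradiol, or men whose testosterone, was out of range are retested. Both hormones are measured, and the start condition is "if estradiol is within postmenopausal range (≤ 30 pg/mL) and testosterone is within the castration range (≤ 50 ng/dL), begin letrozole". Otherwise hormones are retested at C2W1, with a consultation on the start date if they are still out of range.

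The same decision is stated elsewhere as follows.

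- **9.3, Arm C, week 2:** "if estradiol is within postmenopausal range for women or testosterone is within the castration range for men, begin letrozole".
- **9.4, Part 2 (patients coming from Arm A), week 2:** "if estradiol is within postmenopausal range (women) or testosterone is within the castration range (men), begin letrozole".
- **10.0, schedule footnote e:** "If estradiol (females) and testosterone (males) are within castration range. Otherwise, delay start of letrozole until week 4".
- **4.3, Intervention:** blood is drawn one week after leuprolide "to measure serum estradiol levels in females and serum testosterone levels in males". The next bullet starts letrozole "if serum testosterone and estradiol levels are found to be within the castration range", without sex labels.

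Section 4.3 also says that Arm C receives the three drugs "at the same doses and schedule as outlined for Arms A and B". Section 9.3 refers back to 9.1 and 9.2 for the letrozole dose and schedule.

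**The concern.** The Arm B week-2 clause decides when a study drug starts. As worded it imposes a joint condition on both sexes, and the protocol's other start rules in sections 9 and 10 do not. Two conflicts follow if a site applies it literally.

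1. **Between arms.** A man who failed Day 1 and at week 2 has testosterone at or below 50 ng/dL but estradiol above 30 pg/mL starts letrozole in Arm C and is held in Arm B, although the two arms are meant to share a schedule.
2. **Within Arm B.** A man with those same values on Day 1 skips the retest and may start in week 2. A man who first shows them at week 2 is held.

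For such a man the literal rule withholds the aromatase inhibitor because his estradiol is high. Section 3.5.3 attributes about 80% of male estrogen to peripheral aromatization, which is what letrozole blocks. At stake is uniform delivery of the Arm B regimen: two sites could treat the same patient differently, each with text to support it.

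**Working it through.** The plan states no figure to reproduce, so the check compares the rules and then sizes the delay.

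**Step 1. Write each rule as a condition.** E2 = estradiol at or below 30 pg/mL; T = testosterone at or below 50 ng/dL.

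| Source | Sex labels | Condition to start |
|---|---|---|
| 9.2 week 2 (Arm B) | none in the condition | E2 and T |
| 9.2 Day 1 waiver | yes | E2 if female; T if male |
| 9.3 week 2 (Arm C) | yes | E2 if female; T if male |
| 9.4 week 2 (Part 2) | yes | E2 if female; T if male |
| 10.0 footnote e | yes | E2 if female; T if male |
| 4.3 start sentence | none, but follows a sex-specific blood draw | E2 and T if read alone |

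The Day 1 waiver and footnote e also join the hormones with *and*, but their labels assign each hormone to one sex. So the conflict comes from the missing labels, not from the conjunction alone.

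**Step 2. Enumerate the week-2 results.** 2 sexes × 2 estradiol states × 2 testosterone states = 8 combinations.

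| Sex | Estradiol | Testosterone | Arm B, literal | Arm C |
|---|---|---|---|---|
| M | in range | in range | start | start |
| M | in range | high | hold | hold |
| M | high | in range | **hold** | **start** |
| M | high | high | hold | hold |
| F | in range | in range | start | start |
| F | in range | high | **hold** | **start** |
| F | high | in range | hold | hold |
| F | high | high | hold | hold |

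The rules disagree in 2 of 8, always with Arm B stricter. These are logical cells, not a proportion of patients.

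**Step 3. Size the delay.** Leuprolide is given every 4 weeks, so the fallback start at the second dose is nominally day 29. Take the week-2 check as day 8, with day 15 as the late end of its window, and 6 months as 26 weeks = 182 days.

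- Check on day 8: 29 − 8 = 21 days; 21/182 = 11.5%.
- Check on day 15: 29 − 15 = 14 days; 14/182 = 7.7%.

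Under 4.3 and footnote e letrozole starts at week 4. The wait is longer only if the C2W1 consultation in 9.2 sets a later date.

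**The case against.** The strongest reply is that the 9.2 bullet is sex-specific when read whole: it opens by naming women with estradiol out of range or men with testosterone out of range, and the clause can be read as asking whether the value that failed is now in range. Footnote e is explicit and covers the letrozole row of the schedule. This is good evidence of intent. But the opening only defines who is retested; the bullet then orders both hormones and states a two-hormone condition. A site can infer the right rule, but the clause does not state it.

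Second, the discordant patients may be few. Sections 3.5.1 and 5.4 place the hormone flare in the first week and castration by the fourth, so many men will still have high testosterone near day 8 and both rules will hold them. The within-arm conflict needs a man already in the castration range before leuprolide, which is atypical given the 6.3 washout for GnRH agonists. These points limit the frequency. They do not make the patient implausible: section 3.5 describes young men with this tumor, elevated estrogen and tumor aromatase overexpression.

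Third, high estradiol delays letrozole in women in every arm by design, so delay for high estradiol is not in itself an anomaly. That is right. The anomaly is applying it to men in one arm only.

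Fourth, other passages use both hormones jointly: the definition of effective castration in section 14, and the Part 2 rule in 9.4 for continuing leuprolide without letrozole. Neither governs when letrozole starts.

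Finally, the delay percentage has no demonstrated link to PFS6, leuprolide continues meanwhile, and a week-4 start is the ordinary fallback. All of that stands.

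**Conclusion.** The point holds as a minor error of wording. Followed as written, the Arm B week-2 clause contradicts the Arm C and Part 2 rules, footnote e and Arm B's own Day 1 waiver, and nothing in the documents signals that a difference is intended. It delays letrozole by a nominal 14 to 21 days (8% to 12% of 182 days) in two of eight sex-by-hormone combinations.

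This rests on a literal reading by the site, on the nominal days above, and on 6 months taken as 26 weeks. The documents give neither the frequency of such patients nor the effect of the delay on PFS6, so the practical impact is probably small. Sample size, error rates and the two-stage decision rule are unaffected, and no bias in the comparison of Arms B and C is shown.

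**What to change.** In the week-2 bullet of 9.2 and in the start sentence of 4.3, use the Arm C condition, "if estradiol is within postmenopausal range for women or testosterone is within the castration range for men, begin letrozole" 2.5 mg daily, and keep the cutoffs of 30 pg/mL for estradiol and 50 ng/dL for testosterone. Every patient on estrogen deprivation therapy then starts letrozole under one sex-specific rule.

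The cost is one clause and one sentence in an amendment. No tests are added, because both hormones are already drawn at the week-2 retest.

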9.3 Part 1, Arm C: combined everolimus + EDT

- Day 1 of Cycle 1: Baseline serum estrone, estradiol, testosterone and follicle-stimulating hormone (FSH) level in all patients (if not already done). If estradiol is within postmenopausal range for women (≤ 30 pg/mL) and testosterone is within the castration range for men (≤ 50 ng/dL), patient does not have to have hormones retested at week 2 and maybe begin letrozole 2.5 mg po QD Week 2 of Cycle 1.
- Patients will begin leuprolide 7.5 mg IM and everolimus based on BSA:
 - Patients with a BSA $< 1.5 \text{ m}^2$ will receive everolimus 5 mg PO QD.
 - Patients with a BSA $\geq 1.5 \text{ m}^2$ will receive everolimus 7.5 mg PO QD.
- Week 2 of Cycle 1 (+/- 7 days): Women with estradiol not within postmenopausal range (≤ 30 pg/mL) or men with testosterone not within the castration range (≤ 50 ng/dL), measure serum estradiol and testosterone; if estradiol is within postmenopausal range for women or testosterone is within the castration range for men, begin letrozole 2.5 mg po QD. Otherwise, retest hormones on C2W1. Consult MSKCC PI if hormones are still not within range. to further discuss the letrozole start date.
- Leuprolide 7.5 mg IM will be given every 4 weeks (+/- 7 days).
- Everolimus and letrozole will be administered continuously using the same dose, schedule and administration instructions as outlined in sections 9.1 and 9.2. Patients will be given a pill diary to record the date and time that everolimus and letrozole were taken.
- One cycle of combined everolimus + EDT corresponds to 4 weeks of treatment.
- Everolimus, letrozole and leuprolide should be administered concurrently at all times. However, patients who are only able to tolerate everolimus and leuprolide, but not letrozole, can continue on therapy but need to undergo testing of serum estradiol and testosterone every 4 weeks. If serum estradiol remains within the post-menopausal range (in females) or castration range (males), therapy with leuprolide and everolimus continue.
 - Patients who are able to tolerate everolimus and letrozole, but not leuprolide, will be removed

from the study. In very special circumstances (ie. postmenopausal female patient), study chair may allow continuation of everolimus with letrozole pending the approval of the local IRB.

- If everolimus or both EDT drugs must be completely discontinued, patient will be declared off trial. However, if a patient is able to tolerate either component of combined therapy (ie. Everolimus or EDT) but not both, and is experiencing clinical benefit, the study chair may allow continuation of everolimus or EDT pending the approval of the local IRB.
- Treatment will continue until disease progression, global clinical deterioration, unacceptable toxicity and/or consent withdrawal.
- Therapy may be held for a maximum of 4 weeks to recover from toxicity (see Sections 9.5 through 9.8)

9.4 Part 2: Combined therapy with everolimus and EDT after progression on either everolimus or EDT alone

- Patients who develop disease progression on either Arm A or B during Part 1 of the study will proceed to combined therapy.
 - At the start of Part 2 the last CT scan on Part I will be used as the baseline scan for RECIST 1.1 criteria.

Patients who were on everolimus (Arm A) during Part 1 will begin EDT with leuprolide 7.5 mg IM .

- Patients who required a dose reduction on Arm A during Part 1 will continue at the reduced dose level for Part 2.
- Day 1 of Cycle 1: Baseline serum estrone, estradiol, testosterone and follicle-stimulating hormone (FSH) level in all patients. If estradiol is within postmenopausal range for women (≤ 30 pg/mL) and testosterone is within the castration range for men (≤ 50 ng/dL), the patient does not have to have hormones retested at week 2 and maybe begin letrozole 2.5 mg po QD Week 2 of Cycle 1.
 - Week 2 of Cycle 1 (+/- 7 days): Women with estradiol not within postmenopausal range (≤ 30 pg/mL) or men with testosterone not within the castration range measure serum estradiol and testosterone; if estradiol is within postmenopausal range (women) or testosterone is within the castration range (men), begin letrozole 2.5 mg po QD. Otherwise, retest hormones on C2W1. Consult MSKCC PI if hormones are still not within range. to further discuss the letrozole start date.
 - Leuprolide 7.5 mg IM will be administered every 4 weeks (+/- 7 days).

Patients who were on EDT (Arm B) during Part 1 will begin everolimus on Day 1 of Part 2 of the study at the following doses:

- Patients with a BSA $\leq 1.5 \text{ m}^2$ will receive everolimus 5 mg PO QD.
- Patients with a BSA $> 1.5 \text{ m}^2$ will receive everolimus 7.5 mg PO QD.
- Patients should continue with their every 12 weeks hormone testing schedule from Arm B.

All Patients on Part II

- One cycle of treatment with combined therapy corresponds to 4 weeks.
- Everolimus, letrozole and leuprolide should be administered concurrently at all times. However, patients who are only able to tolerate leuprolide, but not letrozole, can continue on therapy but need to undergo testing of serum estradiol every 4 weeks. If serum estradiol remains within the post-menopausal range (in females), therapy with leuprolide and everolimus will continue.
 - Patients who are only able to tolerate leuprolide, but not letrozole, will undergo testing for both serum estradiol and testosterone every 4 weeks. If the levels of these hormones remain within the castration range, therapy on leuprolide will continue.
 - Patients who are able to tolerate everolimus and letrozole, but not leuprolide, will be removed from the study. In very special circumstances, (ie. postmenopausal female patient), study chair may allow continuation of everolimus with letrozole pending the approval of the local IRB.
- If everolimus or both EDT drugs must be completely discontinued, patient will be declared off treatment.
- Treatment will continue until disease progression, global clinical deterioration, unacceptable toxicity and/or consent withdrawal.
- Therapy may be held for a maximum of 4 weeks to recover from toxicity (see Sections 9.5 through 9.8)

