Dual aromatase and mTOR inhibition was evaluated in a phase I trial of letrozole at the standard dose of 2.5 mg PO QD, with two different dose levels of everolimus at 5 mg PO QD or 10 mg PO QD [120]. Safety and pharmacokinetic studies revealed the combination to be safe, with no major interactions at either dose level of everolimus. Only one dose-limiting toxicity, grade 3 thrombocytopenia, occurred in the everolimus 10 mg PO QD cohort. A randomized phase II neoadjuvant breast cancer trial of letrozole 2.5 mg PO QD plus everolimus 10mg PO QD or placebo also reported an acceptable toxicity profile for the combination, with grade 3/4 toxicities occurring in $\leq 5\%$ of patients receiving everolimus [122]. This included three patients who developed pneumonitis which resolved within two weeks of everolimus discontinuation.

EVOLVE-1 is a phase III trial of everolimus at 7.5 mg PO QD versus best supportive care in advanced typical HCC following failure/intolerance of sorafenib (www.clinicaltrials.gov, NCT01035229). The reduced dose of 7.5 mg PO QD was chosen given concerns about pneumonitis at the 10 mg PO QD dose, particularly in a patient population with abnormal hepatic drug clearance. Although most patients with FLL-HCC have normal hepatic parenchyma, hepatic reserve may be somewhat impaired by the presence of tumor. Thus, for the purpose of this trial, everolimus 7.5 mg PO QD will be administered.

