4.1 OVERVIEW OF STUDY DESIGN/INTERVENTION

4.2 Design

This is a multi-institutional randomized three arms phase II clinical trial, consisting of two parts. In Part 1 of this study, patients with advanced (recurrent or metastatic), unresectable FLL-HCC will be randomized to one of three arms: Arm A (everolimus 7.5 mg PO QD); Arm B (EDT with letrozole 2.5 mg PO QD + leuprolide 7.5 mg IM monthly); or Arm C (everolimus + EDT). Upon disease progression, patients in Arm A or Arm B may proceed to Part 2 of the study in which they will receive combination therapy with both everolimus and EDT. Please refer to Figure 1 (page 4) for a schematic of the study design.

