9.1 Part 1, Arm A: everolimus

- Everolimus will be administered by the respective institutions' pharmacies at the following doses:
 - Patients with a BSA $< 1.5 \text{ m}^2$ will receive everolimus 5 mg PO QD.
 - Patients with a BSA $\geq 1.5 \text{ m}^2$ will receive everolimus 7.5 mg PO QD.
- Patients will be instructed to take everolimus at home, at the same time each day, consistently with food or without food, and swallowed whole with a glass of water.
- Patients unable to swallow whole tablets will be instructed NOT to crush or chew them. Instead, they should be completely dissolved in 30 cc of water by gently stirring immediately before swallowing. After swallowing, the glass should be rinsed with another 30 cc of water then swallowed again to make sure the entire dose was administered [131].
- If a dose is missed, they will be instructed to take it as soon as they remember up to 12 hours past the scheduled dose time. If it is almost time to take the next dose, they will be instructed to skip the missed dose and just take the scheduled dose. They will be instructed NOT to take 2 doses at the same time [131].
- If vomiting occurs after taking Everolimus, the subject should not take a replacement dose on that day. The subject should resume taking Everolimus at the next scheduled dose on the following day. If vomiting persists, the subject should be instructed to notify the investigator. If a subject vomits what appears to be an intact tablet(s), the subject should not take a replacement dose on that day because it is not possible to determine how much drug has actually been absorbed.
- Patients will be provided with a pill diary to record the date and time of day that everolimus is taken.
- Everolimus may be held for a maximum of 4 weeks for toxicity (see Section 9.5).
- Treatment will continue until disease progression, global clinical deterioration, unacceptable toxicity and/or consent withdrawal.

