9.5 Everolimus dose modifications and treatment interruptions/discontinuation guidelines

- Renal impairment: No dose adjustment necessary.
- Hepatic impairment: If total bilirubin $> 2 \text{ mg/dL}$, hold treatment for up to 4 weeks, then reduce dose to 5 mg PO daily once total bilirubin $\leq 2 \text{ mg/dL}$.
- Everolimus will be held for any grade 3 hematologic adverse event, grade 2 pulmonary toxicity or any other grade 3 non-hematologic toxicity, excluding hyperlipidemia.

- If recovery (grade 2 or less for hematologic or non-hematologic toxicities) occurs within 4 weeks, everolimus will be resumed at a reduced dose of 5 mg PO daily.
- Any grade ≥ 3 pulmonary toxicity occurring at any time during therapy warrants discontinuation of everolimus and the study chair should be contacted.
- If BSA changes by $> 10\%$ at any time during the study, the dose of everolimus must be adjusted if needed and accordingly.
- Everolimus will not be reduced below 5mg.
- Everolimus may be held for a maximum of 4 weeks from the scheduled date of cycle commencement to permit recovery from toxicities/adverse events as outlined above. If more than 4 weeks are required for recovery, the study chair may allow continuation of everolimus pending the approval of the local IRB.

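### The everolimus dosing text contradicts itself, so patients of the same BSA can be assigned 5 mg or 7.5 mg depending on the section read

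*Combined protocol and SAP*

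**What the plan says.** **Flat dose.** Section 3.8 closes its dose rationale with "Thus, for the purpose of this trial, everolimus 7.5 mg PO QD will be administered". Section 4.2 describes "Arm A (everolimus 7.5 mg PO QD" in the randomization, and section 4.3 repeats "Patients randomized to Arm A will receive everolimus 7.5 mg PO QD". For Arm C, section 4.3 says that patients "will receive everolimus, leuprolide and letrozole at the same doses and schedule as outlined for Arms A and B". None of these mentions BSA.

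**Dose by BSA, Part 1.** Section 9.1 (Arm A) gives 5 mg below 1.5 m² and continues "Patients with a BSA $\geq 1.5 \text{ m}^2$ will receive everolimus 7.5 mg PO QD". Section 9.3 (Arm C) and footnote c of the section 10.0 schedule give the same split. None of the three sets an age limit. Section 5.2 also gives this split, but in the same bullet as, and directly after, a sentence on the dose reported for ages 12 to 18.

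**Dose by BSA, Part 2.** Section 9.4, for patients who were on EDT in Arm B, says "Patients with a BSA $\leq 1.5 \text{ m}^2$ will receive everolimus 5 mg PO QD" and gives 7.5 mg only above 1.5 m².

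**Change in BSA.** Section 9.5 says that if BSA changes by more than 10% "at any time during the study, the dose of everolimus must be adjusted if needed and accordingly". It does not say which BSA the 10% is measured from. Footnote c refers to a change of more than 10% above or below the 1.5 m² "cut-off at any time during the study, the dose of everolimus must be adjusted accordingly".

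**The concern.** The dose a patient receives should follow from the protocol without a choice of section. Here it does not, and the documents do not say whether the overview, the agent description, the treatment plan or the schedule governs.

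The affected BSA range is foreseeable: entry is open from age 12 (section 6.2), and only a BSA below 1 m² is excluded (section 6.3). With four participating centers and at most 28 patients per arm, sites that read different sections could treat like patients differently within one arm.

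The starting dose also determines how the toxicity rules work. Section 9.5 resumes everolimus at 5 mg after a qualifying toxicity and allows nothing below 5 mg. A patient who starts at 7.5 mg therefore has one reduction step, and a patient who starts at 5 mg has none. Under section 14.0, coming off study before the 6-month scan counts as an event for PFS6, so inconsistent dosing could reach the primary endpoint as well as patient safety.

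**Working it through.** No sample size, error rate or event count enters this point, so there is no plan figure to reproduce. The check applies each written rule to the same BSA values.

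**1. Starting dose (mg daily)**

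| BSA (m²) | 3.8, 4.2, 4.3 | 5.2, 9.1, 9.3, footnote c | 9.4 (Arm B entering Part 2) |
|---|---|---|---|
| 1.0 | 7.5 | 5 | 5 |
| 1.2 | 7.5 | 5 | 5 |
| 1.49 | 7.5 | 5 | 5 |
| 1.5 | 7.5 | 7.5 | **5** |
| 1.51 | 7.5 | 7.5 | 7.5 |
| 1.8 | 7.5 | 7.5 | 7.5 |

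- Flat against split: the two disagree for every eligible BSA from 1.0 to below 1.5 m² and agree from 1.5 m² upwards.
- Part 1 split against section 9.4: they disagree only at exactly 1.5 m².
- Size of the disagreement: 7.5 − 5 = 2.5 mg. Relative to the lower dose this is 2.5/5 = 50%; relative to the higher dose it is 2.5/7.5 = one third.

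**2. Change in BSA.** Two assumptions are needed. The 10% in section 9.5 is taken from the starting BSA, and a dose change is needed only when the new BSA falls in the other category of the Part 1 split. Footnote c can be read in two ways.

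*Reading (a): the new BSA must lie more than 10% from the cut-off.* The limits are 1.5 × 0.9 = 1.35 m² and 1.5 × 1.1 = 1.65 m².

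| BSA from → to (m²) | Change | Dose under 9.5 | Dose under footnote c, reading (a) |
|---|---|---|---|
| 1.60 → 1.42 | (1.42 − 1.60)/1.60 = −11% | 5 mg | stays 7.5 mg |
| 1.40 → 1.60 | (1.60 − 1.40)/1.40 = +14.3% | 7.5 mg | stays 5 mg |
| 1.70 → 1.45 | (1.45 − 1.70)/1.70 = −14.7% | 5 mg | stays 7.5 mg |

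All pairs of starting and later BSA from 1.00 to 2.50 m² in steps of 0.01 were compared under these assumptions. Wherever the two rules disagree, section 9.5 changes the dose and footnote c does not. The reverse never occurs.

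*Reading (b): the BSA changes by more than 10% and in doing so crosses 1.5 m².* This is the same condition as section 9.5, and the rules agree in all three examples.

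**3. Missing reference BSA in section 9.5.** Take a patient going 1.60 → 1.52 → 1.42 m². Measured from the start, the change is −11% and the trigger is met. Measured visit to visit, the changes are (1.52 − 1.60)/1.60 = −5.0% and (1.42 − 1.52)/1.52 = −6.6%, and it is never met.

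**The case against.** The best defense is that the flat dose stands only in background (3.8) and overview text (4.2, 4.3), while the treatment plan, the agent section and the schedule footnote all give the same Part 1 split. A site working from section 9 has one starting rule for Part 1. In section 5.2 only the per-m² sentence is expressly limited to ages 12 to 18; the two dosing sentences that follow carry no age limit. This is a reasonable guess at intent, but the documents do not state it. Section 4.3 is written as an instruction and extends the Arm A dose to Arm C. The boundary and BSA-change differences also lie within sections 9 and 10, so giving section 9 precedence over the overview would not settle them.

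Three stronger readings are tempting, and the documents do not support them.

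- A reader might infer that Part 2 re-doses a patient differently from Part 1. It does not. The section 9.4 split applies only to former Arm B patients, who had no everolimus in Part 1. For former Arm A patients, section 9.4 adds EDT and carries forward any reduced dose. Arm C does not enter Part 2.
- A reader might call the Part 2 rule reversed. Its direction is the same throughout; only the placing of exactly 1.5 m² differs, and Part 2 is exploratory.
- A reader might say that section 9.5 and footnote c plainly conflict. Section 9.5 adjusts only where needed, and footnote c admits a reading under which the two agree.

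**Conclusion.** Wrong as written: an internal contradiction in dosing text, in three parts of unequal weight.

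- **Flat dose against BSA split.** This is the widest part and rests on no assumption beyond the text. Any eligible patient from 1.0 to below 1.5 m² is assigned 7.5 mg by one set of sections and 5 mg by the other. The layout of section 5.2 adds doubt about whether the split is meant for adults.
- **Boundary.** The contradiction is certain but narrow. A recorded BSA of exactly 1.5 m² gets 7.5 mg in Arms A and C and 5 mg for an Arm B patient entering Part 2. It is a difference between patients of equal BSA.
- **BSA change.** This is conditional. The rules disagree if footnote c means beyond 1.35 or 1.65 m², and agree if it means a change above 10% that crosses 1.5 m². The missing reference BSA in section 9.5 is a gap under either reading.

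The documents give no BSA distribution, so the number of patients affected is unknown. An effect on PFS6 or on the design's error rates is possible through the route described above, but it cannot be shown from the documents and is not claimed.

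**What to change.** Reconcile sections 3.8, 4.2, 4.3, 5.2, 9.1, 9.3, 9.4, 9.5 and footnote c of section 10.0 so that they give:

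1. one starting-dose rule, with the population it covers (all patients, or an age group) stated;
2. one convention for a BSA of exactly 1.5 m², used in both Parts;
3. one BSA-change rule, with the reference BSA named and with footnote c worded so that it has a single meaning.

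The overview sections can then cross-refer to the governing section instead of restating the dose. Which dose and which rule are right is for the sponsor's clinicians to decide. The cost is a protocol wording amendment. The sample size, the decision rules and the analysis are unchanged.
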